#### Other safety data:

For other safety data, data from early discontinuation should be compared to theoretical visits dates. Only assessments within the window of theoretical date +/-14 days will be used for analyses, if it is planned to have a such assessment at this visit and no other assessment is in the window. If a subject discontinued in the extension treatment period, date will be compared to the theoretical visit dates in extension treatment period as described in Table 3. If a subject discontinued in the extension follow-up period, date will be compared to the theoretical visit dates in extension Follow-up period from Table 4.

For unscheduled safety assessments, if the assessment occurs within a window of theoretical date +/- 14 days for a planned eCRF visit for which it was planned per protocol to have such assessment, and no assessment was done for that visit, the assessment will be assigned to that visit. If the assessment is equally distant from two eCRF visits with no corresponding safety assessment, the assessment will be assigned to the next visit.

Sponsor:	ObsEva		
Protocol:	19-OBE2109-005		
Document Version No.:	1.0	Document Date:	18-MAY-2021

For biopsy, DXA assessment or laboratory assessment, if an assessment has been assigned in external data to a follow-up visit of the main study for subjects who entered in the extension study, the visit of assessment should be reassigned with the same rules described above for unscheduled safety assessment.

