Two analyses were planned: one after all subjects completed the Treatment Period and one after all subjects completed the Post-Treatment Follow-up Period. However, due to the early termination of the study, one summary and report of the data will be performed and will be focused on the safety results from all subjects regardless of treatment duration.

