## Withdrawal during treatment period:

Subjects discontinuing participation in the study during the Treatment Period were to undergo the procedures required at Month 12, except the DXA in case of discontinuation before Month 9 visit. These subjects were to enter the 6-month Follow-Up Period and were to continue daily eDiary recording for 6 months and up to the Month 6 ExFU visit in order to continue to collect efficacy and safety data.

PK sampling was not required if the subject had no IMP administration the day prior to the withdrawal visit.

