## 4.2.12. Last extension treatment administration date, End of extension Study date and Period definitions

The last extension treatment administration date will be defined as the date from the treatment termination reported in the extension period eCRF page. If this date is missing, the last date with a drug intake in the eDiary that is inferior or equal to Month 12 visit or the last available date with a drug intake in the eDiary if the subject discontinued the extension treatment will be used.

For subjects who entered the extension, the end of the extension study date will be the last assessment date in the extension study defined as last assessment recorded in the eCRF (excluding end date of adverse events and concomitant medications) or ediary date.

Note:

- For summaries by visit (efficacy or safety), the Month 6 assessments will be included in the main study analyses. For Adverse Events, Concomitant Medications and Daily diaries data collected on the Month 6 date will be part of the extension for subjects entering the extension study, and will be part of the main Follow-up period for subjects entering the main study follow-up period.
- For Adverse Events, Concomitant Medications and Daily diaries, data collected on the Month 12 date will be part of the Extension Follow-up period for subjects entering the Extension follow-up period.

The extension treatment period will be defined as Month 6 up to (Month 12 date -1) or treatment discontinuation date.

The extension follow-up period will be defined as the Month 12 date or (treatment discontinuation date+1) up to the extension follow-up end date (for subjects who entered the extension follow-up).

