## 4.8.8. Transvaginal Ultrasound (TVUS)

TVUS was to be performed at Month 6, Month 9, Month 12, as well as Month 3 and Month 6 of Extension Follow-up period.

The actual value, change from baseline and change from baseline 2 (only for subjects in the placebo arm in the main study) will be summarized by treatment group for uterus length, width, and depth in mm and corresponding uterine volume in cm3, endometrium thickness in mm.

The number and percentage of subjects with ovarian endometrioma with a diameter of 7 cm or greater, and development of any uterus, left ovary or right ovary abnormality over time will be presented by treatment group.

All TVUS data for each subject will be provided in data listings.

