### 4.8.9.2. Gynecological and Breast examination

Gynecological Examination was to be assessed at Month 6, Month 9 and Month 12, as well as Month 3 of the extension Follow-Up period.

Breast examination (by palpation) was to be performed at Month 6 and Month 12, as well as Month 3 of the extension Follow-Up period.

A summary at each time point will be performed (number and percentage of subjects with normal, abnormal significant) for Gynecological and Breast Examinations.

Results will also be reported in listings.

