- Table 14.4.5.8 Lipids Parameters Shifts from Baseline Based on Clinical Findings from Month 7 up to Month 6 Extension Follow-up – Extension Safety Analysis Set
- Table 14.4.5.9 Lipids Parameters Shifts from Baseline 2\* based on Clinical Findings from Month 7 up to Month 6 Extension Follow-up – Extension Safety Analysis Set – subset of subjects who are in the placebo arm (actual arm) in the main study
- Table 14.4.5.10 Lipids Parameters Shifts from Baseline Based on Normal Ranges from Month 7 up to Month 6 Extension Follow-up – Extension Safety Analysis Set
- Table 14.4.5.11 Lipids Parameters Shifts from Baseline 2\* based on Clinical Findings from Month 7 up to Month 6 Extension Follow-up – Extension Safety Analysis Set – subset of subjects who are in the placebo arm (actual arm) in the main study
- Table 14.4.6.1 Serum levels of P4, SHGB and LH from Month 7 up to Month 6 Extension Follow-up – Extension Safety Analysis Set
- Table 14.4.6.3 Proportions of Subjects with P4 at Least once >10.0 nMol/L from Month 6 to Month 12 Extension Safety Analysis Set
- Table 14.4.7.1 Vital Signs by Visit from Month 7 up to Month 6 Extension Follow-up Extension Safety Analysis Set
- Table 14.4.8.1 Physical Examination Findings from Month 9 up to Month 6 Extension Followup – Extension Safety Analysis Set
- Table 14.4.8.2 Physical Examination Findings Shifts from Baseline from Month 9 up to Month 6 Extension Follow-up – Extension Safety Analysis Set

Sponsor:	ObsEva		
Protocol:	19-OBE2109-00	5	
Document Version No.:	1.0	Document Date:	18-MAY-2021

- Table 14.4.8.3 Physical Examination Findings Shifts from Baseline 2\* from Month 9 up to Month 6 Extension Follow-up – Extension Safety Analysis Set – subset of subjects who are in the placebo arm (actual arm) in the main study
- Table 14.4.9.1 ECG QTcF by Visit from Month 7 up to Month 6 Extension Follow-up Extension Safety Analysis Set
- Table 14.4.9.2 ECG Findings from Month 7 up to Month 6 Extension Follow-up Extension Safety Analysis Set
- Table 14.4.10.1 Gynecological Examination Findings by Visit from Month 9 up to Month 6 Extension Follow-up – Extension Safety Analysis Set
- Table 14.4.11.2 Breast Examination Findings by Visit from Month 9 up to Month 6 Extension Follow-up Extension Safety Analysis Set
- Table 14.4.12.1 Endometrial Biopsy Findings by visit from Month 12 up to Month 6 Extension Follow-up – Extension Safety Analysis Set

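### Under the SAP visit windows, most possible early-termination days leave biopsy and breast results in no on-treatment extension table, and TVUS, other examinations, weight and some DXA scans can lose the termination value

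*SAP*

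**What the plan says.** - **Termination visit.** SAP 4.2.7 states: "Subjects discontinuing participation in the study during the Treatment Period were to undergo the procedures required at Month 12". DXA is excepted before the Month 9 visit. Protocol 10.7.2 says the same.
- **Window rule.** For safety data other than DXA, SAP 4.2.10 states: "Only assessments within the window of theoretical date +/-14 days will be used for analyses, if it is planned to have a such assessment" at that visit and "no other assessment is in the window". A stop during extension treatment is compared with Table 3 only (Month 6, Day 169, to Month 12, Day 337). Unscheduled results follow a similar 14-day rule.
- **DXA.** The same section gives DXA its own windows of 28 days either side of Day 253 (Month 9) and Day 337 (Month 12).
- **Month 6.** SAP 4.2.12 says that for by-visit summaries "the Month 6 assessments will be included in the main study analyses".
- **Planned tests.** SAP 4.8.8: "TVUS was to be performed at Month 6, Month 9, Month 12". SAP 4.8.5 and 4.8.9.2 give the same on-treatment visits for physical examination, weight and gynecological examination. For breast examination, 4.8.9.2 says: "Breast examination (by palpation) was to be performed at Month 6 and Month 12". Biopsy is planned on treatment only at Months 6 and 12, if the endometrium is thicker than 5 mm (4.8.9.1).
- **Tables.** SAP 7.2 lists "Endometrial Biopsy Findings by visit from Month 12 up to Month 6" of extension follow-up. The TVUS, breast, gynecological and physical examination tables start at Month 9. None of these has an end-of-treatment row.
- **Aim.** SAP 2.1 says the single report will be "focused on the safety results from all subjects regardless of treatment duration".

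**The concern.** The study was terminated early, so off-schedule last visits are foreseeable. Endometrial health, gynecological assessments and BMD are stated safety objectives (SAP 1.2). Yet the rule tabulates a termination result only when it happens to fall near a visit at which that test was scheduled.

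For biopsy and breast examination, the only on-treatment slot in an extension table is Month 12. That row would therefore describe almost only women who reached about Month 12. For TVUS, the other examinations and weight, women who stopped before about Day 239 would have no on-treatment row. Some later stoppers would be represented by their Month 9 value and not by their last one. A reader of the tables could take those rows as the on-treatment experience of everyone treated in the extension.

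**Working it through.** **Reproducing the plan's dates.** Theoretical day = 1 + 28 x month. Months 6 to 12 give 169, 197, 225, 253, 281, 309 and 337, which match SAP Table 3.

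**Inputs.** Possible termination days run from 170 to 336, so 336 - 170 + 1 = 167 days. The 14-day windows are Month 6, Days 155-183; Month 9, Days 239-267; Month 12, Days 323-351. Assumption: stop day, termination-visit day and assessment day are the same.

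**Biopsy and breast examination (Months 6 and 12).**
- Days 170-183 can map only to Month 6, which is in no extension table: 14 days.
- Days 184-322 are in no window: 139 days.
- No on-treatment extension row: 14 + 139 = 153; 153/167 = 92%. Only Days 323-336 reach Month 12.

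**TVUS, gynecological and physical examination, weight (Months 6, 9 and 12).**
- In no Table 3 window: Days 184-238 (55) plus 268-322 (55) = 110; 110/167 = 66%.
- Excluding Month 6, because it is in no extension table: 110 + 14 (Days 170-183) = 124; 124/167 = 74%.
- Also counting a Month 9 slot filled on Day 253: Days 254-267 add 14, giving 138; 138/167 = 83%. Moving that visit to Day 256 or Day 250 adds 11 or 17 days instead of 14, giving 135 or 141 (81% or 84%).
- No on-treatment row at all: Days 170-238 = 69; 69/167 = 41%. Later stoppers keep a Month 9 row if that visit was done.

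**DXA (28-day windows).** A termination scan is due from Month 9, so Days 253-336, 84 days. The windows are Days 225-281 and 309-365. Days 282-308 are in neither: 27/84 = 32%.

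**Sensitivity to when women stop.** The documents give no stop dates. The range below puts every stop on Days 170-252 (83 days) or on Days 253-336 (84 days).

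| Outcome | All days | Early stops | Late stops |
|---|---|---|---|
| Biopsy, breast: no on-treatment row | 153/167 | 83/83 | 70/84 |
| TVUS, examinations, weight: no on-treatment row | 69/167 | 69/83 | 0/84 |
| TVUS, examinations, weight: termination value unused, Month 9 on Day 253 | 138/167 | 69/83 | 69/84 |

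**The case against.** The case against has five parts.

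1. **The report's aim is read too strongly.** In context, SAP 2.1 replaces two planned analyses with one. It says whose data enter the report, not that every result gets a table row. That stands. SAP 4.8.2 sends even serious TEAEs by term to listings because numbers are low.
2. **Nothing disappears.** All data are listed (SAP 1.2, 4.2.7). Abnormal findings judged clinically significant, including those that stop treatment, are adverse events (Protocol 12.1.2) and reach those tables. TVUS, physical examination and weight are scheduled again at Months 3 and 6 of follow-up, and gynecological and breast examination at Month 3. Those visits are tabulated. This stands as mitigation, but the values are post-treatment, and a listing gives no rate or denominator.
3. **A Month 12 row should describe women at Month 12.** True, and the by-visit windows should stay. The gap is that no other row takes the termination value.
4. **Stop day is not visit day.** Both documents waive PK sampling if no dose was taken the day before withdrawal, so the visit can come after the last dose. The Month 12 DXA may precede its visit by up to 10 days. The day counts are conditional on this.
5. **SAP 4.2.10 opens by using visits as recorded in the eCRF.** The specific rule for early-discontinuation data governs, and it says only.

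A reader might also infer that adverse biopsy findings are selectively hidden. The documents do not support that. A non-benign biopsy calls for a repeat in follow-up, within the span of the biopsy tables. Whether a benign termination biopsy is repeated depends on whether it counts as the Month 12 biopsy. Uneven loss is possible, not shown.

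**Conclusion.** The gap is real and worth fixing. It is largest for biopsy and breast examination, smaller for TVUS, the other examinations and weight, and partial for DXA, where it comes from a different rule.

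Three limits apply:

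- **Days, not women.** A reader might take 92% as the share of early stoppers without a tabulated biopsy. It is a share of possible stop days, and equals a share of women only if stops were spread evenly. The number and timing of stops are not given. Biopsy is conditional on endometrial thickness, so its tables never cover all women anyway.
- **110 and 124 answer different questions.** A reader might call 124/167 days outside every window. Table 3 includes Month 6, so the literal count is 110; 124 applies only once Month 6 is set aside because its results are reported with the main study.
- **Tables, not the report.** The loss is of on-treatment table rows. Listings, adverse-event tables and follow-up rows remain.

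The mechanism follows from the text. Its effect on this trial's tables cannot be sized from the documents.

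**What to change.** Keep the by-visit windows and add to SAP 4.2.10 and 7.2:

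- **An end-of-treatment row** in the biopsy, breast, gynecological and physical examination, TVUS and weight tables. It takes the last assessment after the first extension dose, up to and including the Month 12 or early-termination visit. Unscheduled results are included and follow-up visits excluded. State a maximum number of days after the last dose for a result to qualify, and show treatment duration and days since last dose beside the row.
- **A worst biopsy diagnosis row** after the first extension dose. First complete the severity order in SAP 4.8.9.1, which gives complex hyperplasia with atypia no place although the same section lists it as a possible result. SAP 4.8.4 already sets a precedent, with a worst on-treatment value, including unscheduled results, for liver tests.
- **The same end-of-treatment row for DXA**, using accepted scans and, where a scan was repeated for a loss of 5% or more, the initial one (SAP 4.8.3). Show treatment duration, and note that no termination scan was required of women who stopped before Month 9.

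Where the termination result is within the stated limit, the untabulated days fall from 153, 138 and 27 to zero. The cost is SAP wording and one or two rows per existing table, with no new data. The downside is that the added rows mix treatment durations. This matters most for BMD, and it is why duration is printed beside them.

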## **Table 3 Theoretical Visit Dates in Extension Treatment Period**

Visit	Theoretical Date
Month 6	Day 169
Month 7	Day 197
Month 8	Day 225
Month 9	Day 253
Month 10	Day 281
Month 11	Day 309
Month 12	Day 337

## **Table 4 Theoretical Visit Dates in Extension Follow-up Period**

Visit	Theoretical Date
Month 1 ExFU	Month 12 or treatment discontinuation date + 28
Month 3 ExFU	Month 12 date or treatment discontinuation date + 84
Month 6 ExFU	Month 12 date or treatment discontinuation date + 168

CRS-BS-TP-000005 V 1.0

Sponsor:	ObsEva		
Protocol:	19-OBE2109-005		
Document Version No.:	1.0	Document Date:	18-MAY-2021

#### 4.2.11. Baseline Definitions

The baseline will be described in two ways:

- Main Baseline, defined in the Statistical Analysis Plan of the main study and calculated according to first dose of IMP taken during the main Study.
- Second Baseline (named Baseline 2), defined as the last assessment before the first active dose of IMP during the extension study. The baseline 2 will be calculated only for the subjects who are in the placebo arm (actual arm) in the main study.

## 4.2.12. Last extension treatment administration date, End of extension Study date and Period definitions

The last extension treatment administration date will be defined as the date from the treatment termination reported in the extension period eCRF page. If this date is missing, the last date with a drug intake in the eDiary that is inferior or equal to Month 12 visit or the last available date with a drug intake in the eDiary if the subject discontinued the extension treatment will be used.

For subjects who entered the extension, the end of the extension study date will be the last assessment date in the extension study defined as last assessment recorded in the eCRF (excluding end date of adverse events and concomitant medications) or ediary date.

Note:

- For summaries by visit (efficacy or safety), the Month 6 assessments will be included in the main study analyses. For Adverse Events, Concomitant Medications and Daily diaries data collected on the Month 6 date will be part of the extension for subjects entering the extension study, and will be part of the main Follow-up period for subjects entering the main study follow-up period.
- For Adverse Events, Concomitant Medications and Daily diaries, data collected on the Month 12 date will be part of the Extension Follow-up period for subjects entering the Extension follow-up period.

The extension treatment period will be defined as Month 6 up to (Month 12 date -1) or treatment discontinuation date.

The extension follow-up period will be defined as the Month 12 date or (treatment discontinuation date+1) up to the extension follow-up end date (for subjects who entered the extension follow-up).

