## 3. SUBJECT POPULATIONS

### 3.1. Analyses Sets Definitions

The following data sets will be used for the statistical analysis:

Extension Safety Analysis Set: All subjects randomized who entered the extension study and received at least one dose of study drug in the extension study irrespective of the treatment received. Subjects will be analyzed according to treatment received

Follow-up Extension Safety Analysis Set: All subjects randomized who entered the extension study and who entered the drug free extension follow-up period. Subjects will be analyzed according to treatment received.

The actual treatment for the extension study will be derived as follows, based on daily e-diary IMP intake data:

Subjects received a different kit of active linzagolix for each month, and a different kit for add-back or placebo for each 3-month period.

The number of days with one pink tablet, one grey tablet and one red capsule taken based on e-diary IMP intake data for each treatment will be computed. Data from "Today" will be used primarily. If data from today is missing, data from "Yesterday" of the following day will be considered. If the e-diary is not completed for a day (neither "Today" nor "Yesterday" of following day), it will be assumed that no drug was taken on that day.

Further rules are as follows:

- Treatment administration errors:
  - If a subject received placebo with placebo ABT on more than 50% of days (even if it is not planned), then the actual treatment group will be placebo with placebo ABT for the extension period.
  - Otherwise, the active treatment (combined with add-back or placebo add-back) with the most days taken will be assigned for the extension period.
  - If the number of days is equal for two treatments groups containing active treatment, then LGX 200 mg with ABT will be assigned for the extension period.
- If a subject discontinued, only data received up to discontinuation will be used.

All analyses for the extension study will be described according to the combined treatment group based on the treatment on the main study and the extension study.

Sponsor:	ObsEva		
Protocol:	19-OBE2109-00	5	
Document Version No.:	1.0	Document Date:	18-MAY-2021

For combined planned treatment groups, the planned treatment during the main study and the planned treatment during the extension study comprise the following four combined planned treatment groups:

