### 4.8.2. Adverse Events

Adverse events will be coded using the Medical Dictionary for Regulatory Activities (MedDRA) and displayed in tables and listings using System/Organ/Class (SOC) and Preferred Term.

Analyses of adverse events will be performed for those events that are considered treatment emergent (TEAEs), where treatment emergent is defined as AEs with a start date on or after the first dose of extension study drug through 30 days after discontinuation of study drug or Month 12 visit date, or any event that was present at Month 6 but worsened in intensity or was subsequently considered drug-related by the investigator through the end of the extension study.

Adverse Event tables will be presented for the following periods: Month 6 to Month 12 (Extension treatment period) and Month 12 to Month 6 ExFU (Extension follow-up period) as defined in section 4.2.12.

Adverse events starting more than 30 days after end of treatment will be considered as post-treatment AE.

For each of these 2 study periods, an overall summary table will be prepared presenting, by treatment group, the number and percentage of subjects with

- any AE,
- any TEAE,
- any post-treatment AE (displayed only for the Extension follow-up period),
- Severe TEAE,
- any TEAE assessed by the Investigator as related to Linzagolix ((definite, probable, or possible relationship),
- any TEAE assessed by the Investigator as related to add-back therapy ((definite, probable, or possible relationship),
- any TEAE leading to permanent discontinuation of IMP,
- any serious adverse event (SAE),
- any serious treatment emergent adverse event (Serious TEAE),
- any serious treatment emergent adverse event (SAE) related to Linzagolix,
- any serious treatment emergent adverse event (SAE) related to add-back therapy,
- any fatal TEAE (where outcome is "Fatal")

CRS-BS-TP-000005 V 1.0

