### Section 14.3.1 Adverse Events

- Table 14.3.1.1.1 Summary of Treatment-Emergent Adverse Events from Month 6 to Month 12 Extension Safety Analysis Set
- Table 14.3.1.1.2 Summary of Treatment-Emergent Adverse Events from Month 12 to Month 6 ExFU - Follow-up Extension Safety Analysis Set
- Table 14.3.1.2.1 Treatment-Emergent Adverse Events by MedDRA SOC and Preferred Term from Month 6 to Month 12 Extension Safety Analysis Set
- Table 14.3.1.2.2 Treatment-Emergent Adverse Events by MedDRA SOC and Preferred Term from Month 12 to Month 6 ExFU Follow-up Extension Safety Analysis Set
- Table 14.3.1.3.1 Non-Serious Treatment-Emergent Adverse Events by MedDRA SOC and Preferred Term from Month 6 to Month 12 Extension Safety Analysis Set (if applicable)
- Table 14.3.1.3.2 Non-Serious Treatment-Emergent Adverse Events by MedDRA SOC and Preferred Term from Month 12 to Month 6 ExFU Follow-up Extension Safety Analysis Set (if applicable)

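### For women who do not enter extension follow-up, TEAEs starting after the treatment period ends reach no TEAE summary table, and no table gives overall TEAE incidence as the SAP defines it

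*SAP*

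**What the plan says.** SAP 4.8.2 has two limbs to its TEAE definition. The first covers events starting from the first extension dose "through 30 days after discontinuation of study drug or Month 12 visit date". The second covers events already present at Month 6 that worsen, or are later judged drug-related, up to the end of the extension study. Beyond that: "Adverse events starting more than 30 days after end of treatment will be considered as post-treatment AE".

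The tables follow a different rule. SAP 4.8.2 states: "Adverse Event tables will be presented for the following periods: Month 6 to Month 12 (Extension treatment period"), with Month 12 to Month 6 ExFU as the second period, both as defined in 4.2.12. That section says: "The extension treatment period will be defined as Month 6 up to (Month 12 date -1) or treatment discontinuation date". The follow-up period is the Month 12 date or "treatment discontinuation date+1) up to the extension follow-up end date (for subjects who entered the extension follow-up". For events dated on the Month 12 visit the only rule is conditional: "data collected on the Month 12 date will be part of the Extension Follow-up period for subjects entering the Extension follow-up period".

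Appendix B of the SAP lists the second-period summary as "Table 14.3.1.1.2 Summary of Treatment-Emergent Adverse Events from Month 12 to Month 6 ExFU - Follow-up Extension Safety Analysis Set". The SOC/preferred-term and non-serious tables for that period use the same set. SAP 3.1 defines it as: "All subjects randomized who entered the extension study and who entered the drug free extension follow-up period".

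**The concern.** The TEAE window runs past the end of the treatment period. Everything after that end is tabulated only for women in the follow-up set. For a woman outside that set, a post-dose event can meet the TEAE definition and still have no table to go into. The overall summary is built separately for each period, so its any-AE, severe, serious, discontinuation and fatal rows omit such an event too.

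TEAE incidence and severity is a named safety endpoint (SAP 2.5.3). SAP 1.2 confines this plan to safety and makes its analyses and tabulations the basis of the study report's results. An event missing from the tables makes the tabulated incidence too low, even if it appears in a listing.

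A related point concerns women who do enter follow-up. Their TEAEs after the last dose appear only in the follow-up tables, so no planned table shows the proportion of women with any TEAE over the defined window.

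**Working it through.** The plan gives no figure on this point, so the check sets the TEAE window against the two periods, day by day.

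Inputs:
- Month 12 falls on Day 337 (SAP Table 3; Protocol 10.2).
- A completer takes her last dose the day before the Month 12 visit, so Day 336 if the visit is on Day 337 (Protocol 10.2.1).
- The early stopper's last dose is on Day D. For illustration I assume D = 253 and take D as her discontinuation date.
- The treatment period ends on Day 336 (completer) or Day D (stopper), by SAP 4.2.12.
- The follow-up period and its tables exist only for women who entered follow-up (SAP 4.2.12, SAP 3.1, Appendix B).
- The phrase that closes the TEAE window in SAP 4.8.2 can be read in three ways for a completer: 30 days from the last dose, 30 days from the Month 12 visit, or closing on the Month 12 visit itself.

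Days inside the TEAE window but in neither period:

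| Woman | Reading of the window | Uncovered days, no entry to follow-up | Uncovered days, entry |
|---|---|---|---|
| Early stopper, D = 253 | D + 30 = 283 | 254 to 283: 283 − 254 + 1 = 30 | 0 |
| Completer | 336 + 30 = 366 | 337 to 366: 366 − 337 + 1 = 30 | 0 |
| Completer | 337 + 30 = 367 | 337 to 367: 367 − 337 + 1 = 31 | 0 |
| Completer | closes on Day 337 | Day 337 only: 1 | 0 |

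Every reading leaves a gap for the non-entrant; only its length changes. Reading the parenthesis in 4.2.12 as limiting just the end date does not help, because the follow-up tables are restricted to the follow-up set.

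The observed gap can be shorter than the window. If a stopper's last contact is a withdrawal visit on Day W, with W no later than D + 30, her observed but untabulated interval is W − D days. A completer last seen at Month 12 has one such day. Events can be captured in this interval: the withdrawal visit follows the Month 12 procedures, including AE recording (Protocol 10.2.1.5 and 10.7.2), and sites report SAEs they learn of up to four weeks after treatment discontinuation (Protocol 12.3.2).

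Overall incidence: let A be the women with a TEAE in the treatment-period table, B those with one in the follow-up table, and C the non-entrants whose only TEAEs fall in the gap. Let N be the size of the Extension Safety Analysis Set and F the size of the follow-up set. The defined incidence is (|A| + |B| − |A and B| + |C|)/N. The planned tables give |A|/N and |B|/F. They give neither the overlap nor C, so the defined incidence cannot be recovered from them.

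**The case against.** The strongest reply is that the gap lies off the planned path. Protocol 10.7.2 and SAP 4.2.7 send women who stop during treatment into the 6-month follow-up, and Protocol 10.2.1.5 does the same for completers. With entry no day is uncovered. The affected events are still reported individually in Listings 16.2.7.1 and 16.2.7.2, and in 16.2.7.3 to 16.2.7.6 where they qualify, all on the full Extension Safety Analysis Set. The SAP already relies on listings for several AE categories because numbers are low, and it plans no hypothesis tests. Splitting entrants' TEAEs by period is a presentation choice that loses nothing.

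Most of this stands and limits the point. It does not remove it: SAP 4.4 counts entry to follow-up as its own row, so entry is not taken as automatic, and a listing does not supply an incidence.

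Several stronger inferences are tempting, and the documents do not support them:
- **That early termination makes non-entry common.** The SAP says only that not all subjects could be followed for time to first menses. It does not say they failed to enter follow-up.
- **That laboratory, ECG, biopsy or DXA findings at withdrawal are lost.** These have their own tables on the full safety set. Early-discontinuation assessments are mapped to planned visits within 14 days, and DXA within 28 days (SAP 4.2.10). DXA is not required on withdrawal before Month 9. In addition, the treatment discontinuation date is not defined separately from the last administration date. If it is recorded at the withdrawal visit, AEs dated that day fall inside the treatment period.
- **That 30 days set against time on drug measures the events lost.** That ratio is a share of a theoretical window, not of events, and AE collection may stop well before day 30.
- **That the loss differs by dose group.** Nothing in the documents shows this.

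**Conclusion.** The gap follows from the SAP's own definitions under every reading of the TEAE phrase. For a woman who does not enter extension follow-up, TEAEs starting after the treatment discontinuation date, or on or after the Month 12 date, reach no TEAE summary table. The uncovered stretch is up to 30 days for a stopper and 1, 30 or 31 days for a completer, depending on the reading. The observed part may be only the days from last dose to last visit.

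This assumes that periods are assigned by event start date and that the discontinuation date is the date of last dose. If that date is recorded later, the gap starts later. The number of women affected is not in the documents. It could be small or zero, so the effect on incidence cannot be sized; its direction, where any such event exists, is to make tabulated incidence too low.

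For women who enter follow-up nothing is lost, but the defined overall TEAE incidence is not shown. Given that safety is the sole focus of this SAP, both points merit correction before the tables are run.

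**What to change.** In SAP 4.8.2 and Appendix B, tabulate all TEAEs as SAP 4.8.2 defines them on the full Extension Safety Analysis Set, whether or not the woman entered follow-up. Keep both limbs: the 30-day window, and events that worsen or are later judged drug-related. There are two ways to do this:
- Add an overall TEAE summary and an overall SOC/preferred-term table. This closes the gap and also supplies the missing overall incidence, so it is the better choice.
- Assign non-entrants' post-dose TEAEs and their Month 12-dated AEs to the treatment period in Tables 14.3.1.1.1, 14.3.1.2.1 and 14.3.1.3.1. This closes the gap but leaves entrants' TEAEs split.

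State one anchor, last dose or Month 12 visit date, for both the TEAE window and the table end date. With mixed anchors, Day 367 of a completer could stay uncovered (337 + 30 = 367 against 336 + 30 = 366).

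Keep the follow-up tables as planned. Reserving them for post-treatment AEs would risk dropping TEAEs from the second limb, and would conflict with the SAP's decision to list post-treatment AEs only, apart from the summary row.

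The cost is a few sentences of SAP text and either two added tables or a changed date filter in three. No new data are needed.
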